4.1.2 Exclusion Criteria

1. Female patients who are of child-bearing potential (defined as a sexually mature woman who has not undergone hysterectomy, bilateral oophorectomy bilateral salpingectomy or bilateral tubal ligation/occlusion, at least 12 weeks prior to screening, or who has not been naturally postmenopausal for at least 24 consecutive months prior to study enrollment) and not using non-hormonal contraception.

2. Female patients not willing to use non-hormonal contraception for one month following treatment.
3. Women who are breast feeding.
4. Female patients who have a positive pregnancy test. [SEP]
5. Female patients with unexplained vaginal bleeding or history of endometrial hyperplasia with atypia or carcinoma. [SEP]
6. Patients with an existing diagnosis of adrenal insufficiency who are on any glucocorticoid replacement other than oral hydrocortisone or prednisone.
7. Patients with hypokalemia < 3.5 mEq/L on lab work completed on Day 1 or obtained within 3 months prior to Day 1.
8. Patients with AST or ALT greater than 3 times the upper limit of normal on lab work completed on Day 1 or obtained within 3 months prior to Day 1.
9. Hypertensive patients with uncontrolled blood pressure defined as SBP > 180 and/or DBP > 100 .
10. Patients on medications that are CYP3A substrates with narrow therapeutic ranges, such as cyclosporine, dihydroergotamine, ergotamine, fentanyl, pimozide, quinidine, sirolimus, and tacrolimus.
11. Patients on medications that are strong CYP3A inhibitors (such as itraconazole, nefazodone, ritonavir, nelfinavir, indinavir, atazanavir, amprenavir, fosamprenavir, boceprevir, clarithromycin, conivaptan, lopinavir, mibefradil, posaconazole, saquinavir, telaprevir, telithromycin, and voriconazole) or inducers (such as rifampin, rifabutin, rifapentine, phenobarbital, phenytoin, carbamazepine, St. John's wort).
12. Patients taking other medications metabolized by CYP3A, such as simvastatin, lovastatin.
13. Patients who are not euthyroid as judged by the investigator.
14. Patients with history of hypersensitivity to mifepristone or the tablet components
15. Patients who have a history of QT prolongation and patients with any recent abnormal ECG.

5 STUDY TREATMENTS

5.1 Allocation to Treatment

All subjects will be in the treatment group.

5.2 Breaking the Blind

Not applicable.

5.3 Drug Supplies-Mifepristone

- Other names for the drug: KORLYM®, C1073, RU486
- Description: 300 mg tablets are light yellow to yellow, oval-shaped, film-coated tablets debossed with “Corcept” on one side and “300” on the other. Each bottle contains 28 tablets.
- Mode of action: Mifepristone is a selective antagonist of the progesterone receptor at low doses and blocks the glucocorticoid receptor (GR-II) at higher doses. Mifepristone has high affinity for the GR-II receptor but little affinity for the GR-I (MR, mineralocorticoid) receptor.

- Pharmacokinetics:

Absorption

Following oral administration of mifepristone to healthy volunteers, time to peak plasma concentrations of mifepristone occurred between 1 and 2 hours following single dose, and between 1 and 4 hours following multiple doses of 600 mg. The mean plasma concentrations of the three active metabolites of mifepristone peak between 2 and 8 hours after multiple doses of 600 mg/day, and the combined concentrations of the metabolites exceed that of the parent mifepristone. Exposure to mifepristone is substantially less than dose proportional. Time to steady state is within 2 weeks, and the mean (SD) half-life of the parent mifepristone was 85 (61) hours following multiple doses of 600 mg/day of mifepristone. Studies evaluating the effects of food on the pharmacokinetics of mifepristone demonstrate a significant increase in plasma levels of mifepristone when dosed with food.

Distribution

Mifepristone is highly bound to alpha-1-acid glycoprotein (AAG) and approaches saturation at doses of 100 mg (2.5 µM) or more. Mifepristone and its metabolites also bind to albumin and are distributed to other tissues, including the central nervous system (CNS).

Metabolism

Cytochrome P450 3A4 (CYP3A4) has been shown to be involved in mifepristone metabolism in human liver microsomes. Two of the known active metabolites are the product of demethylation (one monodemethylated and one di-demethylated), while a third active metabolite results from hydroxylation (monohydroxylated).

Elimination and Excretion

Excretion is primarily (approximately 90%) via the fecal route. Excretion in the urine accounts for less than 10%.

- Side effects: The most common adverse reactions reported in patients with Cushing's syndrome ($\geq 20\%$) include: nausea, fatigue, headache, decreased blood potassium, arthralgia, vomiting, peripheral edema, hypertension, dizziness, decreased appetite, and endometrial hypertrophy. Refer to the current FDA-approved label of Korlym® for the most comprehensive and up to date information on side effects. However, these adverse reactions are observed in patients with Cushing syndrome and are likely due to a contribution by steroid withdrawal syndrome.
- Drug Interactions:
 - CYP3A
 - The use of mifepristone with drugs whose metabolism is primarily mediated by CYP3A (substrates) is likely to result in increased plasma concentrations of the drug. Mifepristone is contraindicated in patients taking simvastatin, lovastatin, and CYP3A substrates with narrow therapeutic ranges. Instructions on handling drugs with high or low first pass metabolism in which CYP3A is the primary or the minor route of metabolism are provided in the current FDA-approved label of Korlym®.
 - Medications that inhibit CYP3A could increase plasma mifepristone concentrations and dose reduction of mifepristone may be required.
 - Mifepristone has not been studied with CYP3A inducers. CYP3A inducers could decrease the plasma concentration of mifepristone and therefore, co-administration should be avoided.
 - Cytochrome P450 (CYP) 2C8/2C9
 - Co-administration of mifepristone with drugs primarily metabolized by CYP2C8/2C9 (substrates) would be expected to result in an increased plasma concentration of that drug. For example, mifepristone significantly increased exposure of the CYP2C8/2C9 substrate fluvastatin. Substrates of these enzymes (e.g., non-steroidal anti-inflammatory drugs, warfarin, repaglinide) should be used at the smallest recommended doses and

monitored closely for adverse effects.

CYP2B6 substrates

- No study has been conducted on the effects of mifepristone on CYP2B6 substrates. Mifepristone is a CYP2B6 inhibitor and may cause significant increase in exposure to drugs that are metabolized by CYP2B6. Caution should be exercised when mifepristone is used concomitantly with CYP2B6 substrates such as bupropion.

Hormonal Contraceptives

- Mifepristone is a progesterone-receptor antagonist and will interfere with the effectiveness of hormonal contraceptives. Therefore, non-hormonal contraceptive methods should be used.

Refer to the current FDA-approved label of Korlym® for the most comprehensive and up to date information on drug-drug interactions with mifepristone.

- **Storage and stability:** Mifepristone tablets should be stored at controlled room temperature, 25°C (77°F); excursions permitted to 15 to 30°C (59 to 86°F). [See USP Controlled Room Temperature]. Mifepristone bottles must be stored in a secure, limited access area.
- **Preparation and Dispensing:** Count the appropriate number of tablets into a prescription bottle and label with a patient-specific label.
- **Administration:** Mifepristone tablets should not be crushed, split, or chewed.
- **Availability:** The investigational drug will be provided by Corcept from the same supply as the commercial drug. Under no circumstance will the study medication, mifepristone, be used other than as directed by the protocol.
- **Return and Retention of Study Drug:** Drug that expires during the study or remains at the site at the end of the study should be discarded on site according to the institutional standard operating procedure for drug destruction. The drug disposition should be documented in the drug accountability logs. The logs including the quantity and lot number of the destroyed drug should be provided to the sponsor.
- **Drug Accountability:** The investigator, or a responsible party designated by the investigator, must maintain a careful record of the inventory and disposition of the investigational drug, mifepristone. The drug accountability records will capture drug receipt, drug dispensing, and final disposition.

5.4 Concomitant medications

Patients on medications listed in the exclusion criteria will not be included in the study.

6 STUDY PROCEDURES- SEE THE SCHEDULE OF ACTIVITIES

6.1 Screening Visit

Potential subjects will be contacted over the phone to review their past medical history and current medications. If the potential participant is a woman of childbearing potential, she will be asked to take an at-home urine pregnancy test or come in for a urine or serum pregnancy test one week prior to visit 1. If they do not meet any pre-screening exclusion criteria, they will present for Day 1 of the study and complete screening labs on this day.

6.2 Treatment Study Period

6.2.1 Visit 1 (Day 1)

Subject will be presented the consent document prior to any procedures on this day. Between 7AM and 9AM, baseline labs, including morning cortisol, ACTH, and other steroid hormones and metabolites (5ml serum, 5ml EDTA) and a serum pregnancy test will be obtained. A comprehensive metabolic panel and complete blood count will be obtained if not already performed in the prior 3 months. Patients will be provided a single dose of 600mg mifepristone to be administered orally, and subjects will be instructed to take the drug between 10PM and 11PM on Day 1. If the participant is scheduled for an ITT as part of their medical care and is consented for this study prior to completing ITT, the study team will attempt to obtain left over blood samples for measurement of baseline labs relevant for

mifepristone testing, if the serum is drawn before 10AM, the lab draw that is part of Day 1 of the study could be omitted in this scenario.

6.2.2 Follow-up

On Day 2, subjects will return to the clinic. It will be confirmed with the participants that they took mifepristone at the recommended time the previous night. We will obtain vital signs. Between 7AM and 9AM, repeat complete blood count (CBC), serum chemistry and hormone labs will be obtained. Adverse events will be collected.

On Day 7 and Day 30, participants will be contacted by phone to assess for any adverse events that occurred since Day 1.

6.2.3 Subjects with history of adrenal insufficiency

Subjects with confirmed history of adrenal insufficiency (AI) on glucocorticoid replacement at baseline will be instructed on the following protocol for glucocorticoid dosing during testing. All components of the study protocol are otherwise the same as above.

- Day 0: Take the morning dose of glucocorticoid and hold the afternoon dose.
 - Day 1: Hold the morning dose until labs are drawn, then take the morning dose.
Hold the afternoon dose.
 - Day 2: Hold the morning dose until labs are drawn, then take the morning dose and resume baseline dosing schedule.
-
- Withholding afternoon doses of glucocorticoids for testing is routinely done in clinical practice and considered safe. Participants with diagnosed AI will be provided with a prescription for 4 mg of dexamethasone. Participants will be

provided with two 24-hour phone numbers to call if/when they experience any side effects. . Participants will be instructed to take 4mg of dexamethasone in case they experience significant signs of acute adrenal insufficiency [increasing nausea, lethargy, diarrhea, fever]. Participants are encouraged to contact one of the 24-hour phone numbers prior to taking the dexamethasone and are advised to call the number after taking the dexamethasone. As participants are scheduled for a blood draw the next morning they will be clinically assessed for adrenal insufficiency in case overnight concerns occur and further management will depend on this clinical evaluation. On day 2, participants with adrenal insufficiency will resume their usual dose of hydrocortisone replacement therapy and occurrence of adrenal insufficiency will become less likely. However, participants will remain advised to keep the dexamethasone emergency dosing and to contact the study team in case of any symptoms and signs of adrenal insufficiency

Table 1. Schedule of Activities

Protocol Activity	Screening Phone Call	Screening / Day 1^a	Day 2	Day 7 (+/- 3 days) Phone Call	Day 30 Phone Call (+/- 3 days)
Visit # / Phone call	1	1	2	3	4
Informed Consent		X			
Medical History	X	X			
Vitals Signs^b		X	X		
Serum Chemistry^c		X	X		
Complete Blood Count		X	X		
Pregnancy Test^d	X	X			
Hormone Labs^e		X	X		
Treatment with study agent (10 pm)		X			
Adverse Event Assessment		X	X	X	X

- a. There will be at least a one-week interval between ITT and mifepristone testing.
- b. Vital signs: height (Day 1 only), weight (Day 1 only), temperature, heart rate, blood pressure.
- c. Serum chemistry: comprehensive metabolic panel. Day 1 labs will be omitted if completed and documented in the patient electronic medical record within the prior 3 months. Day 2 labs will be obtained in all cases.
- d. Urine pregnancy test at home 1 week before scheduled visit or come in to have urine or serum pregnancy test. Day 1 visit will include a Serum pregnancy test (women of childbearing potential)
- e. Hormone labs: ACTH, cortisol and steroid profile (including but not limited to corticosterone, aldosterone, androstenedione, 11-deoxycortisol, 11-deoxycorticosterone, DHEAS, DHEA, 17-hydroxyprogesterone, 17-hydroxypregnenolone). These must be drawn between 7 and 9 AM.

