4.1.1 Inclusion Criteria

Adult (ages ≥ 18 years of age) male and female subjects who:

1. Completed ITT at University of Michigan from 2012 to present.
OR
2. Are scheduled to complete ITT.
OR
3. Are clinically suspected to have adrenal insufficiency but have not undergone ITT.

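### Glucocorticoid holds and rescue dexamethasone depend on an established AI diagnosis, leaving undiagnosed glucocorticoid users with no rule for the Day 2 cortisol and suspected-AI participants with no rescue prescription

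*Combined protocol and SAP*

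**What the plan says.** Section 6.2.3 opens its dose-holding schedule with "Subjects with confirmed history of adrenal insufficiency (AI) on glucocorticoid replacement at baseline will be instructed on the following protocol". Under it, the afternoon dose is skipped on Day 0 and Day 1, and the morning dose waits until after the draw on Day 1 and Day 2. The same section adds: "Participants with diagnosed AI will be provided with a prescription for 4 mg of dexamethasone".

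Eligibility (4.1.1) is wider. It admits anyone with an ITT at the site since 2012 whatever the result, anyone meeting "Are scheduled to complete ITT", and anyone with clinically suspected AI who has had no ITT.

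The only exclusion that names glucocorticoids is number 6 in 4.1.2: "Patients with an existing diagnosis of adrenal insufficiency who are on any glucocorticoid replacement other than oral hydrocortisone or prednisone". Exclusion 12 reads "Patients taking other medications metabolized by CYP3A, such as simvastatin, lovastatin" and does not say whether glucocorticoids are meant. Section 5.4 adds no rule of its own: "Patients on medications listed in the exclusion criteria will not be included in the study".

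Medications are reviewed at the screening call (6.1). On Day 2 the site confirms that mifepristone was taken on time (6.2.2); no question about glucocorticoids is written. Section 9.2.1 compares post-mifepristone cortisol with the ITT peak in all patients.

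**The concern.** The schedule keeps a dose out of the body shortly before the draw. That reason depends on what the participant takes, whereas the rule depends on what has been diagnosed. A participant awaiting ITT who is on empirical hydrocortisone could follow the protocol exactly, take the usual doses, and give a Day 2 sample whose cortisol comes partly from the tablet. If that participant has AI, the test appears to show a response that did not occur.

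The value would enter the correlation with ITT peak and the ROC curve, and the t-tests if the participant is classed as normal ITT or confirmed central AI. ACTH and the steroid profile come from the same draw, so the exploratory analyses share the problem. These are the data meant to inform the post-pilot study.

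The rescue rule raises a separate safety question. Section 5.3 says the study drug "blocks the glucocorticoid receptor (GR-II) at higher doses". A participant with suspected AI may have the disease, yet takes 600 mg without the prescription that diagnosed participants receive.

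**Working it through.** **Planning figures.** 36 months × 365.25/12 ÷ 7 = 156.5 weeks; 156.5/6 = 26.1, so 26 recruited. 26 × 0.85 = 22.1, so 22 with complete data. Both match 9.2.2, and the gap in 6.2.3 changes neither.

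**Who is covered.**

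| Participant on a glucocorticoid | Exclusion 6 applies | Holds | Rescue prescription |
|---|---|---|---|
| Confirmed AI, hydrocortisone or prednisone as replacement | No | Yes | Yes |
| Diagnosed AI, another glucocorticoid as replacement | Yes | – | – |
| Scheduled ITT or suspected AI, no diagnosis | No | No | No |
| Past normal ITT, drug for another illness | No | No | No |

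The last two rows are the gap, unless exclusion 12 is read to cover glucocorticoids.

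**Who can affect the correlation and ROC curve.** An ITT value is needed, so a suspected-AI participant who never has an ITT drops out. Two routes remain:

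- Route 1: mifepristone first, ITT later. Section 6.2.1 describes the opposite order for some ("If the participant is scheduled for an ITT as part of their medical care and is consented for this study prior to completing ITT", leftover ITT blood may replace the Day 1 draw), and section 3 requires only a one-week interval. Neither fixes the order.
- Route 2: a past normal ITT, with a glucocorticoid now taken for another illness.

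**Illustrative size.** The documents give no count of affected participants and no size of a drug effect, so every input except n = 22 is assumed: 11 AI and 11 normal; ITT peak means 10 and 22, SD 3; Day 2 cortisol = ITT peak + noise of SD 4; k Day 2 values in one group replaced by a reading with mean 15, 20 or 25 and SD 5; 20,000 runs per case. With none affected, mean r = 0.863 and the c-statistic is 0.955.

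| Group affected | k | r at 15 / 20 / 25 | Loss in r | c-statistic |
|---|---|---|---|---|
| AI (route 1) | 1 | 0.841 / 0.810 / 0.766 | 0.022 / 0.053 / 0.097 | 0.944 / 0.923 / 0.899 |
| AI (route 1) | 2 | 0.818 / 0.758 / 0.676 | 0.045 / 0.105 / 0.187 | 0.933 / 0.892 / 0.843 |
| Normal ITT (route 2) | 1 | 0.831 / 0.851 / 0.858 | 0.032 / 0.012 / 0.005 | 0.938 / 0.952 / 0.958 |
| Normal ITT (route 2) | 2 | 0.797 / 0.841 / 0.853 | 0.066 / 0.022 / 0.010 | 0.919 / 0.950 / 0.960 |

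A rerun with a different seed agreed within 0.002. With noise SD 3 to 5, the route 1 loss is 0.02 to 0.20. If a route 1 participant's later ITT is normal, the route 2 rows apply.

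**Sensitivity to the model.** With bivariate normal data, true r = 0.7 and n = 22, mean sample r is 0.69 with none affected. Raising two values by 1 to 2 SD gives 0.66 to 0.59 if the two are random, and 0.57 to 0.38 if they have the lowest ITT peaks. Lowering those two lowest by 1 SD gives 0.75, so the bias can go either way.

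**Scale.** For r = 0.7 and n = 22, the 95% interval is tanh(0.867 ± 1.96/√19) = 0.39 to 0.87. In the two-group model with none affected, the sampling SD of r is 0.05.

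**The case against.** No affected participant is shown to exist. Route 1 needs several things at once: an ITT still to come, hydrocortisone without a diagnosis, mifepristone before ITT, and a dose before the draw. The words confirmed, diagnosed and existing diagnosis are not defined as ITT-proven, and the search in 4.1 includes people with AI listed as a clinical diagnosis. A patient on hydrocortisone may carry that label and so be covered already. Medications are reviewed at screening, and 9.2.2 allows for non-analysable specimens. All of this stands and makes the exposed group small, possibly empty. It does not close the gap, because the order of tests is not fixed, the terms are undefined, and no glucocorticoid action follows from the screening review.

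Route 2 is weak. A raised reading in a participant classed as normal does little harm. Strong suppression would do more: readings of 10 or 5 in two normal-ITT participants give r of 0.727 or 0.639, a loss of 0.14 or 0.22. But the direction is uncertain, since 1.4 reports that mifepristone offset a single evening dexamethasone dose, and a two-day hold does not reverse suppression from longer use. Those losses therefore do not support extending the holds.

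A reader might infer that the secondary result will be biased, or that r > 0.7 will be missed. The documents do not support either: no count or effect size is given, and 2.2.2 attaches no test or decision rule to 0.7. A reader might also link the rescue rule to the cortisol readings. Who receives the rescue prescription does not contaminate a sample by itself.

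**Conclusion.** The concern holds as a minor design gap with two separate parts.

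(a) A glucocorticoid user without a diagnosis has no hold and no Day 2 question, so the Day 2 cortisol may reflect the drug. For participants with an ITT value, this reaches the secondary correlation, ROC curve and t-tests and the exploratory hormone analyses. It would be wrong to limit it to the secondary endpoint, because the exploratory assays use the same draw. Recruitment does not depend on it. The true size is unknown: zero if nobody is affected, and about 0.02 to 0.19 in r for one or two affected AI participants of 22 under the two-group assumptions. One affected AI participant at a reading of 15 costs less than one sampling SD of r and at 20 about one; the reading of 25, or two affected at 20 or more, exceeds that.

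(b) On safety, a suspected-AI participant takes the receptor blocker without the rescue prescription. The later instruction in 6.2.3 to take dexamethasone is worded for participants in general, but only diagnosed AI is given the prescription. This part stands on the text and needs no simulation.

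**What to change.** - In 6.2.3, apply the Day 0 to Day 2 holds to participants on oral hydrocortisone or prednisone for confirmed or suspected AI.
- Give the dexamethasone prescription and its instructions to everyone whose doses are held and to all participants with suspected AI.
- In 4.1.2, exclude participants taking systemic glucocorticoids for another illness. This is safer than interrupting that treatment around a receptor-blocking dose, and it makes the reach of exclusion 12 unimportant here.
- At Day 1 and Day 2, record the drug and clock time of the last glucocorticoid dose.
- In 9.2.3, state that a hormone sample drawn after a dose that should have been held is not analysable.

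The cost is a protocol amendment with IRB review (12.2), a few prescriptions, and one question at each of two existing visits. Some suspected-AI participants would skip afternoon doses and delay a morning dose. A few participants or samples may be lost. Lost participants slow recruitment towards 26, and lost samples use up the margin of 26 − 22 = 4 before the complete-data target in the synopsis and 9.2.2 is missed.

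### After the Day 2 visit, participants on glucocorticoid replacement have no scheduled team-initiated contact before the general Day 7 (± 3) call, while a receptor blocker is probably still present

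*Combined protocol and SAP*

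**What the plan says.** Section 6.2.3 of the combined protocol and SAP covers participants with confirmed adrenal insufficiency who take glucocorticoid replacement. Afternoon doses are held on Day 0 and Day 1, and the usual schedule resumes after the Day 2 blood draw: "participants with adrenal insufficiency will resume their usual dose of hydrocortisone replacement therapy". The same sentence adds that "occurrence of adrenal insufficiency will become less likely". The next one keeps the safeguards in place: "However, participants will remain advised to keep the dexamethasone emergency dosing and to contact the study team". Earlier in the section, participants receive a 4 mg dexamethasone prescription and two 24-hour phone numbers, which they may use for any side effect. The symptoms that should prompt dexamethasone are increasing nausea, lethargy, diarrhea and fever.

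Apart from steroid dosing and rescue, this group follows the general schedule: "All components of the study protocol are otherwise the same as above". Under section 6.2.2 and Table 1, that schedule has a Day 2 clinic visit with vital signs, laboratory tests and adverse event collection, then the "Day 7 (+/- 3 days) Phone Call" and a Day 30 call.

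Section 5.3 describes mifepristone as a glucocorticoid-receptor blocker at higher doses. It reports that "the mean (SD) half-life of the parent mifepristone was 85 (61) hours following multiple doses of 600 mg/day of mifepristone" and that, for the three active metabolites, "the combined concentrations of the metabolites exceed that of the parent mifepristone". Both statements come from multiple dosing.

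**The concern.** The reason section 6.2.3 gives for falling risk is the resumed steroid alone. It does not mention that the drug taken about 10 hours earlier blocks the receptor through which that steroid acts. Participants who depend on replacement could have its effect partly opposed for some days while taking no more than their usual dose.

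In that period every route to the team has to be opened by the participant. Recognition may not be easy: two of the four rescue symptoms, nausea and lethargy, resemble reactions listed as common in section 5.3 ("nausea, fatigue, headache, decreased blood potassium, arthralgia, vomiting"), although that list comes from patients with Cushing's syndrome. What is at stake is participant safety in a small, identifiable subgroup. No efficacy or feasibility result is affected.

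**Working it through.** The plan gives no figure for drug persistence after the single dose, so there is nothing to reproduce. Two simple calculations show the size of the issue.

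**1. Parent drug remaining**

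Inputs:
- Dose time: 10 PM on Day 1 (sections 3 and 6.2.1).
- Reference time: 8 AM, the middle of the 7 to 9 AM draw window (section 6.2.2). This gives t = 10 h on Day 2, 34 h on Day 3 and 58 h on Day 4.
- Half-life h: 85 h (section 5.3), with mean − SD = 85 − 61 = 24 h and mean + SD = 85 + 61 = 146 h as the range.

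Formula: fraction remaining = 0.5^(t/h).

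| Time | h = 24 h | h = 85 h | h = 146 h |
|---|---|---|---|
| Day 2, t = 10 h | 74.9% | 92.2% | 95.4% |
| Day 3, t = 34 h | 37.5% | 75.8% | 85.1% |
| Day 4, t = 58 h | 18.7% | 62.3% | 75.9% |

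Assumptions: the multiple-dose half-life applies to one dose, decline is single-exponential, absorption is ignored, and active metabolites are not counted. Later days are not relied on, because the range becomes too wide to be useful.

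**2. Gap to the next team-initiated contact after the Day 2 visit**

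- The call window is Day 7 − 3 = Day 4 to Day 7 + 3 = Day 10.
- Nominal gap: 7 − 2 = 5 days. Earliest: 4 − 2 = 2 days. Latest: 10 − 2 = 8 days.
- With an added call on Day 3 or Day 4: 3 − 2 = 1 day or 4 − 2 = 2 days.
- The Day 7 and Day 30 calls do not move, so no later gap lengthens.

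On these assumptions, most of the parent drug is present when usual dosing resumes, even at the short half-life (about 75%). The days with the highest residual fraction after the Day 2 visit are those without a scheduled contact.

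**The case against.** The strongest reply is that the protocol already manages this risk. All participants are seen in clinic on Day 2, and section 6.2.3 adds a clinical assessment for adrenal insufficiency if there were overnight concerns. Rescue dexamethasone and the advice to call continue with no end date. Because the 24-hour numbers are for any side effect, a participant who takes nausea for a drug reaction is still told to call; correct self-diagnosis is not needed to reach the team. This stands, and it makes the point a modest one. It does not change the fact that these routes all wait for the participant to act.

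A second reply is pharmacological. Section 5.3 reports exposure that is less than dose proportional and protein binding that approaches saturation, so simple decay of parent drug is a weak proxy for active drug. The evidence in section 1.4 concerns morning ACTH and cortisol, not clinical adrenal insufficiency. This also stands: clinically relevant blockade over several days is plausible but not established by the documents.

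A third is that one call would miss onset on Day 5 or 6, still relies on reported symptoms, and could fall on the same day as a Day 7 call made at the start of its window. That is true. The call shortens the first gap; it does not remove the risk.

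**Conclusion.** The point holds as a cheap safety improvement. After the Day 2 visit, participants on replacement have no scheduled, team-initiated contact for nominally 5 days (2 to 8 by the window), while taking their usual steroid dose with a receptor blocker probably still present. The illustrative residual is 92% (75 to 95%) on Day 2, falling to 62% (19 to 76%) on Day 4, under the assumptions listed with the calculation.

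A reader might infer more, and the documents do not support it:
- That these participants have no study-team contact before Day 7. They attend the Day 2 clinic visit.
- That the sentence in section 6.2.3 is wrong. It is comparative, naturally read against the night of withheld steroid, and may be right; it only leaves drug persistence out of its reasoning.
- That the continuing risk is ignored. The very next sentence keeps the rescue and the advice to call.
- That the percentages measure receptor blockade. No figure in the documents links plasma level to blockade or to symptoms.

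**What to change.** In section 6.2.2 and a footnote to Table 1, add for participants treated under section 6.2.3 a study-team phone call on Day 3, or Day 4 at the latest. The caller asks about each symptom listed in 6.2.3 (increasing nausea, lethargy, diarrhea, fever) and about any dexamethasone use, and refers any positive answer to the investigator for clinical evaluation. Keep the Day 7 and Day 30 calls; the added call does not replace the Day 7 call.

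Optionally, add to the 6.2.3 sentence that receptor blockade may persist after replacement resumes, without stating a duration, since the documents give none. On its own this wording would change nothing in practice; the call is the substantive change.

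The cost is one line and one footnote, with no new visit, sample or dosing change. The downside is one extra call per participant on replacement: at most 26 over 36 months at the target enrolment of 26, and fewer in practice because only some participants are on replacement.
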